In vivo monkey PK data from the GLP toxicology study [Report_SL2020IB001] were used to convert the target Cmax to a human equivalent dose (HED). In the monkey GLP toxicology study, a dose of 1 mg/kg was associated with a mean Cmax of 1230 ng/mL (13.96 nM, n=6 monkeys). Note that the lowest dose studied in the GLP study was 0.1 mg/kg; however, the Cmax was not well characterized as only two animals had measurable concentrations at this dose level. The non-quantifiable concentrations were likely due to the rapid clearance of SL-172154 from the serum. Potential explanations for rapid drug clearance include an antigen sink due to the ubiquitous expression of CD47 on peripheral blood cells (i.e., RBC, platelets, PBMC) and target-mediated uptake at early time points with trafficking of cells (e.g., PBMC) and bound drug to peripheral tissues. From Day 15 onwards, the removal of drug by anti-drug antibodies results in rapid

CONFIDENTIAL Compound: SL-172154

clearance. Assuming dose-proportionality, a dose of 0.4 mg/kg in the monkey is predicted to achieve the preliminary human target Cmax (5.18 nM). The 0.4 mg/kg dose level in monkeys was converted to a HED using a standard conversion factor of 0.32 [FDA, 2005]. The resultant preliminary starting dose for IV infusion of SL-172154 in humans is 0.1 mg/kg (0.4 mg/kg x 0.32).

The GLP study concluded that 1.0 mg/kg was considered to be NOAEL for IV infusion doses of SL-172154. Thus, the proposed SL-172154 starting dose of 0.1 mg/kg is 1/10th the NOAEL dose of 1 mg/kg observed in cynomolgus monkeys and provides an appropriate safety margin for the FIH starting dose.

Justification for Schedule: A weekly dosing schedule for 5 consecutive weeks was implemented in the NHP studies. Toxicity was dose-dependent (only at the higher doses) and occurred at the third and subsequent doses. Receptor occupancy data from Day 1 (Dose 1) demonstrated that SL-172154 readily bound to its intended target in a dose-dependent manner, attaining >90% CD40 receptor occupancy on PBMCs and ~80% CD47 receptor occupancy on RBCs in the 10 and 40 mg/kg groups. Maximal occupancy for the CD47 receptor on RBCs was attained by 1 hour postinfusion and persisted through at least 168 hours. CD40 receptor occupancy was transient, likely influenced by endocytosis and migration of CD40+ cells to tissues including the spleen.

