9.1 Data Handling

The nominal time relative to the start of infusion will be calculated as the planned time relative to the end of infusion plus the planned infusion duration. The actual time relative to the start of infusion will be calculated as the actual sampling time relative to the start of infusion (SOI) or the SOI of the first infusion period if with infusion interruption(s). Missing PK sampling time will be handled as the following when calculating the actual time relative to SOI:

- If a sampling time is missing and no infusion interruption, the actual time relative to SOI will be calculated as time from SOI to end of infusion (EOI) plus planned time relative EOI.
- If a sampling time is missing and there is interruption(s) during the infusion, the actual time relative to SOI will be calculated as time from the SOI of first infusion period to the EOI of the last infusion period plus planned infusion time relative to EOI.

Concentration values that are below the limit of quantification (BLQ) will be handled as the following:

- If a BLQ value occurs at the predose, the BLQ value will be assigned as zero concentration. If one or more BLQ values occur in a profile after infusion but before the first measurable concentration, the BLQ values will be assigned a value of zero concentration. For linear plots, zero concentration value(s) will be included in the plot. For log-linear plots, zero concentration value(s) will be assigned a missing value.
- If a BLQ value occurs after a measurable concentration in a profile and is followed by a measurable concentration, then the BLQ will be set as missing.
- If a BLQ value occurs after the last measurable concentration in a profile, then the BLQ values will be set as missing.
- If two or more BLQ values occur in succession after a measurable concentration, the profile will be deemed to have terminated at the first BLQ value (BLQ values will be set to missing) and any subsequent concentration will be set as missing.
- BLQ values that are set to be missing will be omitted from PK parameter generation, concentration summary, and the individual PK profile plots.
- For the time point that all concentrations are BLQ and all BLQ results are imputed to be zero, then the mean/median concentration will be reported as zero.

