9.3 PK Parameters

The PK parameters will be derived from the concentration-time data using the actual collection time from SOI. The PK parameters will be calculated by standard non-compartmental analysis (NCA) as data permits. At least one post-dose concentration is required for C_{max} calculation, and at least three consecutive post-dose concentrations are required for AUC parameter calculation.

Table 6 SL-172154 PK Parameters

C _{max}	Maximum observed concentration over a dosing interval
C_{trough}	Observed concentration at the end of a dosing interval.
T _{max}	Time of maximum observed concentration
AUC _{0-last}	The area under the serum concentration time curve, from time 0 to the last
	quantifiable concentration, calculated by a combination of linear and
	logarithmic trapezoidal methods (Linear up/log down method).
AUC_{0-inf}	Area under the serum concentration time curve from time 0 extrapolated to
	infinity, calculated as AUC _{last} + C _{last} /terminal elimination rate constant (λz).
	Reliability of AUC _{0-inf} values is contingent on the percent of the total area
	obtained by extrapolation: AUC _{0-inf} values with <20% of the total area
	coming from Clast/λz are considered acceptable. Any exceptions to the above
	procedures will be clearly documented/justified in the PK report.

AUC _{tau}	The area under the serum concentration time curve over the dosing interval, calculated by a combination of linear and logarithmic trapezoidal methods (Linear up/log down method).
%AUCext	Percentage of AUCo-inf due to extrapolation from Tlast to infinity
t _{1/2}	Terminal elimination half-life, estimated using the equation $[\ln(2)/\lambda_z]$
CL	Clearance; calculated as Dose/AUC _{0-inf} for C1D1 and Dose/AUC _{tau} for later time unless specified otherwise
Vz	Volume of distribution, calculated as Dose/ $(\lambda_z * \text{AUC0-inf})$ for C1D1 and Dose/ $(\lambda_z * \text{AUC}_{tau})$ for later time unless specified otherwise
AR _{AUCtau}	Accumulation ratio of AUC _{tau} (C1D15/C1D1 and C2D1/C1D1).
AR _{Cmax}	Accumulation ratio of C _{max} (C1D15/C1D1and C2D1/C1D1).

The elimination rate constant (λ_z) will be determined if the log-linear terminal elimination phase is apparent and excludes C_{max} . The λ_z will only be considered reliable if the adjusted coefficient of determination (adj-R²) is greater than or equal to 0.8. Parameters dependent on λ_z (i.e., $t_{1/2}$, AUC_{0-inf}, AUC_{%ext}, CL, Vz) will not be presented if λ_z cannot be estimated.

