9.4 Assessment of Dose Proportionality

An assessment of dose proportionality will not be based strictly on statistical rule criteria but rather, several factors will be considered when assessing dose proportionality, such as results derived from a Power Model (e.g., the slope estimate, and the width of the 95% confidence intervals), graphical evaluation (box plots of dose-normalized PK parameters) and descriptive statistics of PK parameters by dose, as data permit.

Dose normalized PK parameters will be calculated by dividing total administered dose (mg) for AUC_{0-inf}, AUC_{0-last}, AUC_{tau}, C_{max}, and C_{trough}. Additional dose normalized PK parameters may be calculated, if appropriate and as data permit. Dose proportionality will be evaluated graphically using box plots of dose normalized PK parameters (AUC_{0-inf}, AUC_{0-last}, AUC_{tau}, C_{max}, and C_{trough}) by dose level for C1D1, C1D15 and C2D1.

Dose proportionality will also be evaluated for the AUC_{0-inf}, AUC_{0-last}, AUC_{tau}, C_{max}, and C_{trough} using the power model as data permit. A statistical linear relationship between the ln-transformed PK parameters and the ln-transformed actual dose received in mg will be fitted by using a mixed effect model with ln-transformed dose as a fixed effect and subject as random effect. Additional predictors may be included in the model. The general form of the power mode is described as:

$$Ln(Y) = \beta_0 + \beta Ln (Dose) + \varepsilon$$

where Y represents the pharmacokinetic parameter. Note that $\beta = 1$ would correspond to perfect dose proportionality.

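### The dose-proportionality model takes the log of Ctrough, but troughs below quantification are set to zero or missing, so they drop out mainly at low doses and bias the estimated slope downward

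*SAP*

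**What the plan says.** SAP 9.4 fits the log of each PK parameter on the log of the dose in mg, with subject as a random effect: "A statistical linear relationship between the ln-transformed PK parameters and the ln-transformed actual dose received in mg will be fitted". Five parameters are listed, ending with "and C_{trough} using the power model as data permit". A slope of 1 "would correspond to perfect dose proportionality". The section sets no decision rule: "An assessment of dose proportionality will not be based strictly on statistical rule criteria". It weighs the slope, the width of its 95% CI, box plots and descriptive statistics.

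SAP 9.3 defines Ctrough as "Observed concentration at the end of a dosing interval", which in practice is the next predose sample. SAP 9.1 has two rules that can apply to a BLQ trough:

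- Predose: "If a BLQ value occurs at the predose, the BLQ value will be assigned as zero concentration".
- Tail of the preceding profile: "If a BLQ value occurs after the last measurable concentration in a profile, then the BLQ values will be set as missing".

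SAP 9.1 gives the lower limit of quantification (LLQ) as 10 ng/mL. It makes zeros missing on log-linear plots but does not say what happens to them in the log regression. No substitution rule, censored-data method or count of excluded subjects is given for SAP 9.4.

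**The concern.** A zero has no logarithm and a missing value contributes nothing, so a BLQ trough leaves the model under either rule. The planned doses span 100-fold (0.1 to 10 mg/kg), so the losses fall mostly on the low dose levels. The subjects who remain there have the highest exposures. The low-dose end of the line is raised and the slope flattens. Proportional troughs can then look less than proportional, and troughs that rise more than proportionally can look closer to proportional.

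Protocol 3.2 gives a reason to take low-dose BLQ values seriously. In monkeys at 0.1 mg/kg, the trial's starting dose, "the Cmax was not well characterized as only two animals had measurable concentrations at this dose level". Possible explanations given there include rapid clearance and a CD47 antigen sink. With planned cohorts of about three subjects, losing one or two at a low dose level can move the fit.

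**Working it through.** **Inputs from the documents.** Five dose levels of 0.1, 0.3, 1, 3 and 10 mg/kg (SAP 3.1). 21 subjects if only Schedule 1 is evaluated (SAP 3.3). LLQ 10 ng/mL (SAP 9.1). Monkey Cmax at 1 mg/kg of 1230 ng/mL = 13.96 nM, and a human target Cmax of 5.18 nM (Protocol 3.2). Monkey half-lives of 0.4 to 1.1 h (Protocol 1.2.4). Human half-life expected to be below 30/5 = 6 days (Protocol 4.1, criterion 10).

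**Assumptions.** The 21 subjects are split 3/3/3/6/6. Decline is mono-exponential and the trough is at 7 days (168 h). Volume and half-life each have a log-SD of 0.25. The starting concentration at 0.1 mg/kg is either 1230 x 0.1 = 123 ng/mL or 5.18 x 1230/13.96 = 456 ng/mL.

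**Typical trough.** C = C0 x (dose/0.1) x 2^(-168/T), where T is the half-life. For example, at T = 24 h and C0 = 123, the 0.1 mg/kg trough is 123 x 2^(-7) = 0.96 ng/mL and the 1 mg/kg trough is 9.6 ng/mL, just under the LLQ.

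**Slope when the true slope is 1.** With no LLQ the fit returns 0.99-1.01, which reproduces the SAP's reference. The table shows the fit with values below 10 ng/mL dropped.

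| Half-life | Typical trough at 0.1 mg/kg (C0 = 123 / 456), ng/mL | Lowest level with typical trough at or above 10 ng/mL (C0 = 123 / 456) | Mean slope, BLQ dropped |
|---|---|---|---|
| 18 h | 0.19 / 0.71 | 10 / 3 mg/kg | 0.44-0.55 |
| 24 h | 0.96 / 3.6 | 3 / 0.3 mg/kg | 0.65-0.75 |
| 36 h | 4.8 / 18 | 0.3 / 0.1 mg/kg | 0.85-0.94 |
| 48 h | 10.9 / 40 | 0.1 / 0.1 mg/kg | 0.93-0.99 |

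A second run of the same set-up, including a 33-subject split, gave 0.38-0.53, 0.61-0.74 and 0.84-0.93 at 18, 24 and 36 h, and 0.92-1.00 at 48-72 h.

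**Without a half-life assumption.** Here the median trough at 0.1 mg/kg is set directly, with a log-SD of 0.3 to 1.0 and weight about 70 kg:

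| Median trough at 0.1 mg/kg | Share BLQ overall | Mean slope, BLQ dropped |
|---|---|---|
| 10 ng/mL | 7-10% | 0.98-0.89 |
| 3 ng/mL | 23% | 0.97-0.79 |
| 1 ng/mL | 36-38% | 0.95-0.68 |
| 0.3 ng/mL | 60-61% | 0.78-0.49 |

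At 30 ng/mL or more the slope is 0.96-1.00. A mixed model with a random subject effect, as SAP 9.4 specifies, shows the same bias: 0.95, 0.91 and 0.84 at 10, 3 and 1 ng/mL with moderate variability.

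**Monkey-like half-lives.** The highest monkey mean Cmax, 727,000 ng/mL, needs log2(72,700) = 16.1 half-lives to reach 10 ng/mL. At 1.1 h each, that is about 18 h. Every weekly trough would be BLQ and no slope could be fitted.

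**Censored fit.** A quantified trough contributes the normal density of ln(C) about b0 + b ln(dose). A BLQ trough contributes the normal probability that ln(C) is below ln(10). This gives a median slope of 0.98-1.06 in the half-life scenarios, and 0.95-1.04 for median troughs of 0.3 ng/mL or more. At 0.1 ng/mL (83-88% BLQ) it gives 0.51-0.76 where it can be fitted at all, so it is not usable there either.

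**The case against.** The strongest reply is that nothing formal depends on this slope. SAP 9.4 has no test of slope 1. It names interval width as an input, fits the model only where the data allow, and adds plots and descriptive statistics. In the 18 h scenarios, 0-2% of 0.1 mg/kg troughs and 1-15% of 0.3 mg/kg troughs are quantifiable, and the median interval width is about 1.3-2.4. A careful reader would see that such a slope is uninformative. All concentrations, BLQ included, are listed under SAP 9.2, and box plots of Ctrough by dose level are planned. This stands, and it limits the consequence. It does not remove the bias in the middle range, where the interval is narrower and the slope looks usable.

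A reader might infer four stronger things that the documents do not support:

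- **That proportionality is falsely rejected at some rate.** There is no rejection rule, so error rates and power would describe a procedure the SAP does not contain.
- **That the AUCs suffer the same selection.** SAP 9.3 needs three consecutive post-dose concentrations, and Protocol 6.1.1 samples intensively over the first hours. Under the assumptions above, the typical 0.1 mg/kg concentration 4 h after the starting value is still 123 x 2^(-4/18) = 105 ng/mL, so essentially nobody is lost. Monkey-like clearance could change that, but then the trough model is not run.
- **That the recommended Phase 2 dose is directly affected.** That choice rests on the totality of the data, and no section ties it to this slope.
- **That low-dose troughs will be BLQ in humans.** The monkey statement concerns Cmax, not human troughs. It also makes the linear scaling to 123 ng/mL uncertain.

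Exclusion of zeros from the regression is itself an inference, because the SAP is silent. The alternative is a substitution that the SAP does not specify.

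**Conclusion.** The concern holds for Ctrough. Applying the SAP's BLQ rules and then its log-scale model drops low values at low doses and biases the slope downward. The bias is large when the lower dose levels straddle 10 ng/mL, small from a half-life of about 48 h upward for 7-day troughs, and moot when nearly all troughs are BLQ. On Schedule 1 the interval from C1D15 to C2D1 is 14 days. Under mono-exponential decline, ignoring carry-over, a 14-day trough at half-life T behaves like a 7-day trough at T/2. The 24-36 h results would then apply to that trough at 48-72 h.

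These sizes rest on assumed human half-lives, starting concentrations and variability. What is affected is one parameter in a supportive PK assessment; no primary conclusion depends on it.

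**What to change.** In SAP 9.4, for Ctrough only:

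- Fit the power model by maximum likelihood with BLQ troughs treated as left-censored at 10 ng/mL, in place of the zero or missing values from SAP 9.1.
- Report the number of BLQ subjects at each dose level beside the slope and its 95% CI.
- Do not report a slope when nearly all troughs are BLQ (about 80% or more), because the censored fit is also unreliable there. Describe the data instead.

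The cost is one SAP paragraph and slightly more programming. Intervals will be wider where censoring is heavy, which reflects the information actually available.

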10. PHARMACODYNAMIC AND BIOMARKER ANALYSES

The analysis plan for pharmacodynamic and biomarker data will be provided in a separate analysis plan.

11. CHANGE FROM PROTOCOL-SPECIFIED ANALYSES

There are four changes from protocol-specified analyses:

- 1. Protocol Section 9.2.3 states that tabular summaries will be presented by dose levels/schedule/cohorts. Due to the limited enrollment, data from different cohorts will be pooled and summarized by schedule/dose level.
- 2. It is clarified in SAP Section 4 that the DLT Evaluable Population derivation is for the subjects enrolled in the dose escalation cohorts.
- 3. It is clarified in SAP Section 4 that all subjects who have signed the main study inform consent form are defined as Screened population, instead of Enrolled population.
- 4. "postdose" was added in SAP Section 4 for the definition of PK Population.

13. APPENDIX: LIST OF TABLES, FIGURES AND LISTINGS

13.1 List of Tables

ICH Heading	Table Number	Table Description	Analysis Population
14.1		Demographics	
	14.1.1	Study Populations and Subject Disposition	All Screened
	14.1.2	Study Treatment Status	All Treated
	14.1.3	Protocol Deviations	All Treated
	14.1.4	Demographic and Baseline Characteristics	All Treated
	14.1.5	Study Cancer History	All Treated
	14.1.6	Prior Anti-Cancer Treatment	All Treated
14.2		Efficacy	
	14.2.1	Objective Response with Confirmation Based on RECIST 1.1	All Treated
	14.2.2	Objective Response with Confirmation Based on RECIST1.1	Response Evaluable
	14.2.3	Objective Response with Confirmation Based on iRECIST	All Treated
	14.2.4	Time to Response and Duration of Response Based on RECIST 1.1	Response Evaluable
	14.2.5	Time to Response and Duration of Response Based on iRECIST	Response Evaluable
	14.2.6	Progression-Free Survival Based on RECIST 1.1	All Treated
	14.2.7	Progression-Free Survival Based on iRECIST	All Treated
	14.2.8	Overall Survival	All Treated
	14.2.9	Tumor Assessment at Baseline	All Treated
	14.2.10	CA-125	All Treated
14.3		Safety	
14.3.1		Study drug exposure/adverse event	
	14.3.1.1	Study Drug Exposure	All Treated
	14.3.1.2	Overall Summary of Treatment-Emergent Adverse Events	All Treated
	14.3.1.3	All Treatment-Emergent Adverse Events by System Organ Class and Preferred Term	All Treated
	14.3.1.4	All Treatment-Emergent Adverse Events by Preferred Term and Maximum Toxicity Grade	All Treated
	14.3.1.5	Drug-Related Treatment-Emergent Adverse Events by Preferred Term and Maximum Toxicity Grade	All Treated
	14.3.1.6	All Treatment-Emergent Adverse Events by Preferred Term	All Treated
	14.3.1.7	Serious Treatment-Emergent Adverse Events by Preferred Term	All Treated
	14.3.1.8	Immune Related Treatment-Emergent Adverse Events by Preferred Term	All Treated

ICH Heading	Table Number	Table Description	Analysis Population
	14.3.1.9	Drug-Related Treatment-Emergent Adverse Events by Preferred Term	All Treated
	14.3.1.10	Drug-Related Serious Treatment-Emergent Adverse Events by Preferred Term	All Treated
	14.3.1.11	Treatment-Emergent Adverse Events with Toxicity Grade 3 or 4 by Preferred Term	All Treated
	14.3.1.12	Dose Limiting Toxicities	DLT Evaluable
	14.3.1.13.1	Treatment-Emergent Adverse Events leading to Infusion Interrupted by Preferred Term	All Treated
	14.3.1.13.2	Treatment-Emergent Adverse Events Leading to Dose Not Given/Held by Preferred Term	All Treated
	14.3.1.13.3	Treatment-Emergent Adverse Events Leading to Drug Interrupted by Preferred Term	All Treated
	14.3.1.14	Treatment-Emergent Adverse Events leading to Drug Withdrawn by Preferred Term	All Treated
	14.3.1.15	Summary of Drug-Related Infusion Related Reaction at Subject Level	All Treated
	14.3.1.16	Summary of Drug-Related Infusion Related Reaction at Event Level	All Treated
	14.3.1.17	Summary of Drug-Related Infusion Related Reaction by Dosing Visit	All Treated
	14.3.1.18	Deaths	
14.3.5		Laboratory	
	14.3.5.1	Hematology – Maximum CTCAE Grade Shift from Baseline	All Treated
	14.3.5.2	Chemistry – Maximum CTCAE Grade Shift from Baseline	All Treated
	14.3.5.3	Coagulation and Thyroid Function Test – Maximum CTCAE Grade Shift from Baseline	All Treated
	14.3.5.4	Laboratory Tests without CTCAE - Maximum Shift from Baseline with Respect to Normal Range	All Treated
	14.3.5.5	Post-Baseline Potential Serious Hepatoxicity	All Treated
	14.3.5.6	Summary of Change for Select Laboratory Tests	All Treated
14.3.6		Other Safety Data	
	14.3.6.1	ECOG Performance Status – Maximum Shift from Baseline	All Treated
14.3.7		PK	
	14.3.7.1	SL-172154 Serum Concentration-Time Data	PK
	14.3.7.2	SL-172154 PK Parameters	PK

13.2 List of Figures

ICH Heading	Figure Number	Figure Description	Analysis Population
14.2	14.2.1	Horizontal Bar Plot of Duration on Treatment by Response	All Treated
	14.2.2	Waterfall Plot of Target Lesions Maximum Reduction in Sum of Lesion Diameters	All Treated
	14.2.3	Plot of Target Lesions Percent Change from Baseline Sum of Lesion Diameters Over Time	All Treated
	14.2.4	Kaplan-Meier Plot of Time to Response Based on RECIST 1.1 and iRECIST	Response Evaluable
	14.2.5	Kaplan-Meier Plot of Duration of Response Based on RECIST1.1 and iRECIST	Response Evaluable
	14.2.6	Kaplan-Meier Plot of Progression-Free Survival Based on RECIST1.1 and iRECIST	All Treated
	14.2.7	Kaplan-Meier Plot of Overall Survival	All Treated
	14.2.8	Plot of Percent Change from Baseline for CA-125 Over Time	All Treated
14.3	14.3.7.1	Plot of Individual SL-172154 Concentration-time Profiles by Dose Level (Linear and Semi-log)	PK
	14.3.7.2	Plot of Individual SL-172154 Concentration-time Profiles with Infusion Time by Dose Level (Semi-log)	PK
	14.3.7.3	Plot of Mean (+/-SD) SL-172154 Concentration-time Profile by Dose Level (Linear and Semi-log)	PK
	14.3.7.4	Plot of Median (Min-Max) SL-172154 Concentration-time Profile by Dose Level (Linear and Semi-log)	PK
	14.3.7.5	Plot of Mean (+/-SD) Dose Normalized SL-172154 Concentration-time Profile by Dose Level (Linear and Semi-log)	PK
	14.3.7.6	Box Plot of C _{max} by Dose Level	PK
	14.3.7.7	Box Plot of Dose Normalized C _{max} versus Dose Level	PK
	14.3.7.8	Box Plot of AUC _{0-last} versus Dose Level	PK
	14.3.7.9	Box Plot of Dose Normalized AUC _{0-last} versus Dose Level	PK
	14.3.7.10	Box Plot of C _{max} versus Visit for Each Dose Level	PK
	14.3.7.11	Box Plot of AUC _{0-last} versus Visit for Each Dose Level	PK
	14.3.7.12	Box Plot of Dose Normalized AUC _{0-inf} versus Dose Level	PK
	14.3.7.13	Box Plot of Dose Normalized AUC _{tau} versus Dose Level	PK
	14.3.7.14	Box Plot of Dose Normalized Ctrough versus Dose Level	PK

